## **9 STUDY TREATMENT DISCONTINUATION AND PARTICIPANT DISCONTINUATION/WITHDRAWAL**

### **9.1 Discontinuation of Trial**

This study may be temporarily suspended or prematurely terminated by the Sponsor if there is sufficient reasonable cause. Written notification documenting the reason for study suspension or termination by the Sponsor will be provided to investigators or the Sponsor, respectively; study participants; the Institutional Review Board (IRB); and regulatory authorities. Study participants will be contacted, as applicable, and be informed of any changes to the study visit schedule.

Circumstances that may warrant termination or suspension include, but are not limited to:

- Determination of unexpected, significant, or unacceptable risk to participants
- Demonstration of efficacy that would warrant stopping
- Insufficient compliance to protocol requirements
- Data that are not sufficiently complete and/or evaluable
- Determination that the primary endpoint has been met
- Determination of futility
- Failure to meet enrollment goals overall or at a particular trial site

The study may resume once concerns are addressed to the satisfaction of the Sponsor, IRB, and/or regulatory authorities.

### **9.2 Participant Discontinuation/Withdrawal from the Study**

Patients are free to withdraw from participation in the study at any time upon request. A patient may be withdrawn from the study by the Investigator or designee and not be allowed to continue the study if any of the following occur:

- Withdrawal of consent by the patient
- Withdrawal of patient at the discretion of the Investigator or designee if concurrent illnesses occur that may invalidate the study data or are considered to increase the risk from the study participation
- Discovery that the patient has entered the study in violation of the inclusion/exclusion criteria stated in the protocol
- Significant critical protocol violation occurs during the study
- Pregnancy

The reason for discontinuation or withdrawal from the study will be recorded. Patients who sign the ICF and are discontinued or withdrawn from the study should visit the clinic for EOT procedures shown in the SoA ([Section 3.3](#)). Samples and data collected from patients up to the point of discontinuation/withdrawal may still be included in the analyses.

### **9.3           Lost to Follow-Up**

A patient will be considered lost to follow-up if he or she fails to return for scheduled visits and is unable to be contacted by the study site staff. If a patient fails to return to the clinic for a required study visit, the site will attempt to contact the patient and reschedule the missed visit and ascertain if the participant wishes to and/or should continue in the study.

Before a participant is deemed lost to follow-up, the Investigator or designee will make every effort to regain contact. These contact attempts should be documented in the participant's medical record or study file.

## 10 STUDY ASSESSMENTS AND PROCEDURES

### 10.1 Efficacy Assessments

The following efficacy parameters will be measured:

- Tumor response according to RECIST, version 1.1: ORR, DoR, PFS (at Screening and every 6 weeks from Cycle 1 Day 1 until progression)
- Biomarker analysis: ctDNA (at Screening and every 2 cycles until progression)

#### 10.1.1 Tumor Assessment (RECIST v1.1)

Tumor assessment (RECIST version 1.1) will be performed at Screening and every 6 weeks from Cycle 1 Day 1 until progression of disease, EOT, or until the patient commences further anti-cancer treatment, whichever comes first.

- Imaging may be performed within 7 days before the scheduled visit.
- In the event of a delay or discontinuation of study drug, tumor assessment should continue to follow the original schedule.

The Investigator will choose the anatomical extent and the modality of imaging study, while brain MRI is mandatory at screening. The assessment by the Investigator/local radiologist will be the basis for eligibility, continuation, or discontinuation of the trial in an individual patient.

[REDACTED]

[REDACTED]

[REDACTED]

[REDACTED]

[REDACTED]

[REDACTED]

[REDACTED]

#### 10.1.2 Circulating Tumor DNA Assessment

[REDACTED]

[REDACTED]

[REDACTED]

[REDACTED]

[REDACTED]

[REDACTED]

[REDACTED]

[REDACTED]

### 10.1.3 Tumor Biopsy

#### **10.1.3.1 Archival Tumor Blocks Taken Before the Study**

Term	Percentage
GDP	100
Inflation	98
Interest rates	97
Central bank	96
Monetary policy	95
Quantitative easing	94
Inflation targeting	93
Interest rate hike	92

### 10.2.3 Adverse Events and Other Safety Assessments

For details of AE assessment refer to [Section 10.6](#).

[REDACTED]

[REDACTED]

[REDACTED]

[REDACTED]

[REDACTED]

### 10.2.3.1 Laboratory Tests

Laboratory tests includes:

Complete blood count with differential, platelet count and ANC

Plasma: total protein, albumin, creatinine, blood urea nitrogen (BUN), uric acid, bilirubin (total and direct), alkaline phosphatase, alanine aminotransferase (ALT), aspartate aminotransferase (AST), gamma glutamyltransferase (GGT), glucose, calcium, phosphorus, chloride, sodium, potassium, magnesium, serum amylase, serum lipase, and coagulation tests (prothrombin time [PT] or international normalized ratio [INR], activated partial thromboplastin time [aPTT]).

Serology (at Screening): hepatitis B surface antigen (HBsAg), Anti-hepatitis C virus (HCV), HIV test

Urine: glucose, protein, blood

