### 4.3 Risk/Benefit Assessment

#### 4.3.1 Known Potential Risks

In preclinical toxicity studies conducted to date, BBT-176 was negative for in vitro toxicity as assessed by hERG patch clamp, AMES, and micronucleus testing. The animals receiving BBT-176 showed similar class effects as other EGFR TKIs and dose-related toxicological findings including clinical signs, body weights, food consumption, clinical pathology parameters, organ weights, gross pathology, and histopathological examination, with similar toxicity overall compared with brigatinib (for details, refer to the Investigator's Brochure). Therefore, potential risks based on its mechanism of action may be similar to those reported for other EGFR TKIs. For example, brigatinib can cause severe, life-threatening and fatal pulmonary adverse reactions consistent with interstitial lung disease (ILD)/pneumonitis, hypertension, bradycardia, elevated creatine phosphokinase and pancreatic enzymes, hyperglycemia, and embryo-fetal toxicity based on animal reproduction studies, as reported in its Prescribing Information [[Prescribing Information of Alunbrig \(brigatinib\)](#)]. Osimertinib, a kinase inhibitor indicated for the treatment of patients with metastatic *EGFR* T790M mutation-positive NSCLC who have progressed on or after EGFR TKI therapy, can cause ILD/pneumonitis, prolongation of the corrected QT (QTc) interval, cardiomyopathy, and embryo-fetal toxicity based on animal reproduction studies, as reported in its Prescribing Information [[Prescribing Information of Tagrisso \(osimertinib\)](#)].

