##### **5.3.1.1 Primary Endpoint**

- Safety and tolerability (incidence of adverse events [AEs] and clinical laboratory abnormalities defined as DLTs)

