## **10.6 Adverse Events and Serious Adverse Events**

### **10.6.1 Definition of Adverse Events (AE)**

The descriptions found in the revised NCI CTCAE version 5.0 will be utilized for AE reporting. In case of AE(s), investigators may perform unscheduled clinical examination(s), intervention(s), etc. for AE management.

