### 11.7 Safety Analysis

Safety variables to be assessed will include AEs, laboratory test results (hematology, clinical chemistry, and urinalysis), ECG, weight, and vital signs.

Adverse event terms recorded on the eCRFs will be mapped to preferred terms using the Medical Dictionary for Drug Regulatory Activities (MedDRA®) version 23.0 or later. The number and percentage of patients with AEs will be summarized for each dose level and overall according to the system organ class and preferred term. Adverse events (including AESI) will be summarized for overall frequency (number and percentage of patients), worst reported severity, and relationship to study treatment for each preferred term per patient. Serious adverse events will be similarly summarized. Listings of deaths, SAEs, and AEs leading to early termination of study treatment or premature withdrawal from study will also be provided.

Laboratory variables will be summarized using actual values and changes from baseline to scheduled time points. Laboratory values will also be categorized according to their CTCAE (v5.0) toxicity grade and tabulated by worst on-study toxicity grade. The baseline value of a variable is defined as the last value obtained on or before the date and time of the first BBT-176 dose.

ECG, weight, and vital signs will also be summarized by actual values and changes from baseline to scheduled time points using descriptive statistics. Changes in QTcF will also be evaluated for the proportion of patients with absolute values > 500 msec and change from baseline > 60 msec.

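### Elevated creatine phosphokinase (CPK) is cited as a possible risk, but CPK is not in the listed laboratory panel, so symptom-free rises would not be systematically found

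*Protocol*

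**What the plan says.** Protocol section 4.3.1 summarises the animal toxicology as resembling the class, "with similar toxicity overall compared with brigatinib". It concludes that "potential risks based on its mechanism of action may be similar to those reported for other EGFR TKIs" and gives two marketed drugs as examples. The reactions listed for brigatinib include "bradycardia, elevated creatine phosphokinase and pancreatic enzymes, hyperglycemia".

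Protocol section 10.2.3.1 sets out the laboratory tests analyte by analyte. The blood chemistry part names 19 analytes (bilirubin counted once). Glucose is among them, and the line closes with "serum amylase, serum lipase, and coagulation tests". CPK is not named. The visit lists that remain legible under section 10.5 ask only for laboratory tests and carry no separate CPK line.

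Three other provisions bear on what happens to a laboratory finding:

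- Section 5.3.1.1 makes adverse events and "clinical laboratory abnormalities defined as DLTs" the Part 1 primary endpoint.
- Section 11.7 and SAP section 10.3 summarise laboratory variables as values and changes from baseline, and grade them by CTCAE v5.0, "tabulated by worst on-study toxicity grade".
- Section 10.6.1 states that, when an adverse event occurs, "investigators may perform unscheduled clinical examination(s), intervention(s), etc. for AE management". Section 10.6.5 has laboratory changes that the investigator judges clinically significant recorded as adverse events.

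**The concern.** The risk section and the laboratory panel do not match. The panel takes up the other laboratory risks in the brigatinib sentence and leaves out the one named next to pancreatic enzymes, and the readable text gives no reason.

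CPK elevation is a laboratory finding. Where it causes no symptoms, adverse event reporting will not bring it to light unless someone measures it. Without a scheduled value before and during treatment, the laboratory tables would say little about a risk that the protocol itself raises. An absence of reported rises could mean that none occurred or that nobody looked. This matters most in Part 1, where safety and tolerability are a primary objective and, under section 12.8, the Safety Monitoring Committee uses safety findings in choosing the next dose.

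**Working it through.** No arithmetic in the plan is at issue, so the check sets the sections side by side and follows a CPK rise through the reporting rules.

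**1. Laboratory risks against the panel**

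| Laboratory risk named for brigatinib (4.3.1) | Analyte in 10.2.3.1 |
|---|---|
| Elevated pancreatic enzymes | serum amylase, serum lipase |
| Hyperglycemia | glucose |
| Elevated CPK | none |

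Two of three are covered; 3 − 2 = 1 is not.

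**2. Any other place that schedules CPK.** In the readable text of both documents, CPK appears only in section 4.3.1. The Schedule of Activities tables, the Part 1 visit procedures, the general text of 10.2.3 and the contents of the dose adjustment table are redacted or not shown, so they can be neither counted for nor against.

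**3. A rise with symptoms.** The investigator may order a CPK test under 10.6.1. If the result is judged clinically significant, 10.6.5 makes it an adverse event, 10.6.3.1 grades it by CTCAE v5.0, and 11.7 tabulates it by worst severity. It is therefore detected, graded and counted as an adverse event. It does not reach the laboratory summaries, because SAP section 4.1 limits summary tables to scheduled assessments; it appears in the listings. There would usually be no pre-dose value to compare it with.

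**4. A rise without symptoms.** Nothing in the readable plan prompts a test. There is no scheduled baseline and no scheduled on-treatment value. Change from baseline and worst grade (11.7, SAP 10.3) cannot be formed, and section 11.3 rules out imputing missing values. The rise is missing from the laboratory tables, the adverse event tables and the safety data sent to the committee, unless a site happens to measure CPK.

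**5. Size of the under-count.** Let π be the true proportion of patients with a CPK rise and s the fraction of those rises that lead to a test for any reason. The proportion that the study can detect is

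 π × s,

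and the proportion missed is π × (1 − s). The documents give neither π nor s. The detected proportion lies between 0 (s = 0) and π (s = 1), so no figure for the shortfall can be derived. The patients affected would include the up to 48 planned for dose escalation (11.1.1) and those in the later cohorts.

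**The case against.** A reader might infer that CPK toxicity cannot be detected, graded or counted at all, that its observed incidence is zero at every dose, and that the MTD and RP2D would be set blind to it. The documents do not support this, for four reasons.

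- **There is another route.** Unscheduled testing and the rule on clinically significant results let a symptomatic or incidentally found rise be recorded and graded. This stands and removes any claim of zero incidence. It does not help with rises that nothing prompts anyone to look for.
- **The DLT criteria are redacted.** Whether a CPK rise, in particular a symptom-free one, would count as a dose-limiting toxicity or is excluded cannot be seen. The link to the primary endpoint's laboratory component, and from there to the MTD and RP2D, is therefore unverified. This stands in full.
- **Other text is hidden, and the list may be open-ended.** A CPK test could sit in the redacted Schedule of Activities, and the introduction to the panel does not say that the list is complete. This lowers certainty. However, the panel itself is unredacted and specific down to total and direct bilirubin, and the legible visit lists add nothing to it. If CPK is scheduled elsewhere, the panel should agree. If it is left to site choice, ascertainment would differ between sites, since section 10.4 has safety tests done by each site's own laboratory.
- **The risk is borrowed.** CPK elevation is reported for brigatinib, not observed with BBT-176. The animal data are deferred to the Investigator's Brochure, and section 10.6.8 does not make CPK an event of special interest. This stands as to the strength of the signal. It does not explain why the panel covers the other two laboratory risks in the same sentence and not this one.

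**Conclusion.** The point holds in a limited form. In the readable plan, CPK elevation is named as a risk that BBT-176 may share, and CPK is not in the listed panel. One of three laboratory risks in that sentence has no scheduled baseline or on-treatment measurement. Symptom-free rises would not be systematically ascertained and would be under-counted in the laboratory tables and in the data that the Safety Monitoring Committee reviews.

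The conclusion assumes that the panel in 10.2.3.1 governs the scheduled chemistry tests, that no CPK test is hidden in redacted text, and that some CPK rises occur without symptoms. The last is not stated in the documents. The size of the under-count is unknown. No consequence for DLT counts, the MTD or the RP2D can be claimed. This is a low-cost improvement and an inconsistency to reconcile, not a flaw that undermines the safety analysis.

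**What to change.** Reconcile section 4.3.1 with section 10.2.3.1 by adding creatine phosphokinase to the chemistry list, measured on the chemistry samples already planned and including one before the first dose. CPK would then enter the existing change-from-baseline and worst-grade tables in section 11.7 and SAP section 10.3 with no new statistical method. If the redacted Schedule of Activities already contains CPK, the list needs only to be brought into line. If the sponsor has a reason for omitting it, stating that in 4.3.1 would settle the inconsistency, though symptom-free rises would still go unmeasured.

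The cost is one more analyte at the local laboratories, with protocol and eCRF wording. The downside is that some incidental rises unrelated to the drug will need grading; the pre-dose value helps to interpret them. Patients already on treatment when the change takes effect may lack a baseline, and their change from baseline would stay missing under section 11.3. No dosing or management rule needs to change.

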#### **10.2.3.2      ECG**

Twelve-lead ECG will be performed at the visit indicated in the SoA ([Section 3.3](#)). The timing and number of ECGs may be altered depending on the emerging PK and safety profile.

Twelve-lead ECGs will be obtained after the patient has been resting supine or semi-supine for at least 10 minutes prior to times indicated. All ECGs should be recorded with the patient in the same physical position. Screening, Day 1 of each Cycle, EOT, and Safety F/U visit. Serial ECGs will be conducted on Cycle 1, Day 1 pre-dose and at 2 ( $\pm 10$  min), 4 ( $\pm 15$  min), and 6 ( $\pm 15$  min) h post-dose, on Day 2 prior to discharge. When ECGs are scheduled at the same time as blood draws, the ECGs will be obtained prior to and as close to the scheduled blood draw as possible. For screening and each time point of Cycle 1, ECG recording should be repeated 3 times with an interval of about 5 minutes. Single ECG recording will be taken from Cycle 2. A standardized ECG machine should be used, and the patient should be examined using the same machine throughout the study if possible.

From version 5.0. ECG on Day 2 is not applicable.

After ECGs have been recorded, the Investigator or designated physician will review each of the ECGs and may refer to a local cardiologist if appropriate. A copy should be filed in the patient's medical records. If an abnormal ECG finding at Screening or baseline is considered to be clinically significant by the Investigator, it should be reported as a concurrent condition. For all ECGs, details of rhythm, ECG intervals, and an overall evaluation will be recorded.

#### **10.2.3.3      Echocardiogram/Multiple-gated Acquisition (MUGA) Scan**

[figure not shown]
At Screening: only patients with suspect cardiac disease with negative effect on ejection fraction (EF) will be measured during Screening according to local standards at the Investigator's discretion (e.g., echocardiogram or MUGA). Echocardiogram or MUGA scan within 6 months is accepted for screening assessment.

During the study and safety follow-up visit, if physical or lab findings suggest cardiac damage, echocardiogram or MUGA should be done.

## 10.3 Pharmacokinetics

Venous blood samples will be collected to measure the BBT-176 concentrations in plasma as well as the following PK parameters:

- $T_{1/2}$  (Part 1 only)
- $C_{max}$
- $T_{max}$
- AUC (Part 1 only)
- $C_{trough}$  (Part 1 only)

The timing of the PK samples may be adjusted during the study, dependent on emerging data, in order to ensure appropriate characterization of the plasma concentration-time profiles.

A 10-minute window will be allowed for samples taken at 1 hour; a 20-minute window for samples taken at 2 to 8 hours; and a 1-hour window for samples taken at 12 and 24 hours. In case of divided dosing, blood collection time must be measured from the time of the first divided intake.

Details about blood sample collection, preparation of sample, storage/shipment, and disposal will be provided in the laboratory manual.

## 10.4 Volume of Blood

The number of samples taken, as well as the volume required for each analysis, may be changed during the study as new data become available. The estimated total volume of blood that will be

drawn from each patient in this study for mandatory samples up to the end of Cycle 2 is approximately [REDACTED]

Safety laboratory assessments will be performed locally at each site's laboratory by means of their established methods. The number of samples/blood volumes is therefore subject to site-specific change.

## 10.5 Study Procedures

[figure not shown]
The first dose of each cycle is considered Day 1 of each cycle, and cycles will repeat every 21 days unless there is a treatment delay. Please refer to 3.3 Schedule of Activities (SoA) for each visit window.

### 10.5.1 Part 1 (Dose-Escalation and RP2D Exploratory Cohort, Phase 1)

A horizontal bar chart illustrating the distribution of 1500 data points across 15 categories. The categories are represented by horizontal bars of varying lengths, with the longest bar reaching approximately 1400 on the y-axis. The bars are ordered from longest to shortest, with the first category at the top and the last at the bottom. The distribution is highly skewed, with most categories having fewer than 100 data points.

Category	Approximate Data Points
1	1400
2	1300
3	1200
4	1100
5	1000
6	900
7	800
8	700
9	600
10	500
11	400
12	300
13	200
14	150
15	100

This document is confidential.

A horizontal bar chart illustrating the distribution of 1000 samples across 10 categories. The categories are represented by horizontal black bars of varying lengths. The x-axis is labeled 'Category' and the y-axis is labeled 'Sample ID'.

[figure not shown]
Category	Sample ID	Length (approx.)
1	1	100
1	2	100
1	3	100
1	4	100
1	5	100
1	6	100
1	7	100
1	8	100
1	9	100
1	10	100
2	1	100
2	2	100
2	3	100
2	4	100
2	5	100
2	6	100
2	7	100
2	8	100
2	9	100
2	10	100
3	1	100
3	2	100
3	3	100
3	4	100
3	5	100
3	6	100
3	7	100
3	8	100
3	9	100
3	10	100
4	1	100
4	2	100
4	3	100
4	4	100
4	5	100
4	6	100
4	7	100
4	8	100
4	9	100
4	10	100
5	1	100
5	2	100
5	3	100
5	4	100
5	5	100
5	6	100
5	7	100
5	8	100
5	9	100
5	10	100
6	1	100
6	2	100
6	3	100
6	4	100
6	5	100
6	6	100
6	7	100
6	8	100
6	9	100
6	10	100
7	1	100
7	2	100
7	3	100
7	4	100
7	5	100
7	6	100
7	7	100
7	8	100
7	9	100
7	10	100
8	1	100
8	2	100
8	3	100
8	4	100
8	5	100
8	6	100
8	7	100
8	8	100
8	9	100
8	10	100
9	1	100
9	2	100
9	3	100
9	4	100
9	5	100
9	6	100
9	7	100
9	8	100
9	9	100
9	10	100
10	1	100
10	2	100
10	3	100
10	4	100
10	5	100
10	6	100
10	7	100
10	8	100
10	9	100
10	10	100

## Safety Follow-up

Safety follow-up should be performed 3 [REDACTED] after the last administration of study drug or immediately before initiation of any other cancer therapies.

- Complete physical examination, including measurement of weight, auscultation of the heart for new development of murmur (if physical or lab findings suggest cardiac damage, echocardiogram or MUGA should be done)
- ECOG performance status
- Vital signs
- Laboratory tests
- Serum pregnancy test in female patients of childbearing potential
- 12-lead ECG
- Concomitant medications

- Complete physical examination, including measurement of weight, auscultation of the heart for new development of murmur (if physical or lab findings suggest cardiac damage, echocardiogram or MUGA should be done)
- ECOG performance status
- Vital signs (including blood pressure, heart rate, respiratory rate, and temperature)
- Laboratory tests: pre-dose
- Serum pregnancy test in female patients of childbearing potential
- 12-lead ECG: pre-dose
- Return BBT-176 and diary review
- BBT-176 and diary distribution
- Whole blood sampling for ctDNA (every 6 weeks from Cycle 1 Day 1, within 7 days from Day 1 of odd number of cycles [Cycles 3, 5, 7, and so on])
- RECIST version 1.1 tumor assessment (every 6 weeks from Cycle 1 Day 1, within 7 days from Day 1 of odd number of cycles [Cycles 3, 5, 7, and so on])
- Concomitant medications
- AE assessments

